# F.2 Aim 2: Determine if insular TMS alters insular connectivity:

F.2.1 Statistical Design: A second-level random effects model will be used to compare insular connectivity by treatment and group using ANCOVA. Age will be controlled for as nuisance variables. A Monte Carlo cluster correction threshold will be applied to correct for multiple comparisons, using a voxel-wise p<0.005 and family-wise p < 0.05.

F.2.2 Sample Size and Power Analysis: Hanlon et al. measured fMRI connectivity changes after rTMS to two separate prefrontal targets, resulting in Cohen's *d* values greater than 1.9. Based on these estimates, our target recruitment goal must be greater than 6 in each arm (total n=12) to detect significant differences with 80% power and 0.05 significance level. Our sample size n=32 (after 10% attrition of fMRI data, 10% attrition of TMS administration) is similar or larger compared to other studies using similar methods. With a sample size of 32, we can detect a correlational effect size as small as 0.30 ( $f^2$ ) with 80% power and 0.05 significance level.

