# IV. Research Methods

**A. Outcome Measure(s):** Outcome measures will include (1) cigarette craving measures, (2) resting-state fMRI connectivity measures, and (3) tasked-based fMRI insular activity measures.

A.1 Neuropsychological Testing: Our primary cognitive outcome will be the change after treatment compared to before treatment in the Questionnaire of Smoking Urges – Brief Version (QSU-brief), a measures craving. An additional important question is whether craving, smoking history, smoking characteristics, or personality traits are associated with specific changes in connectivity after treatment. Thus, we will perform the following assessments prior to treatment: (1) smoking history questionnaire, (2) Fagerstrom nicotine dependence scale (FNDS), (3) Wisconsin inventory of smoking dependence motives (WISDM-68), (4) behavioral inhibitory scale and behavioral activation scale (BIS/BAS), (5) Barratt impulsiveness scale (BIS-11). The QSU-brief will be administered before and after treatment. A visual analog scale will be used to quickly assess subjects' craving during the craving visual-cue task:

The craving data before and after treatment will be used to investigate Aim #1.

A.2. Magnetic Resonance Imaging. All MRI scans will be acquired using a 3.0 T Seimens Skyra MR system using a 20-channel head-neck coil. High-resolution 3D T1-weighted scans will be acquired before treatment for image registration and normalization. T2\* weighted echo-planar imaging blood oxygen level dependent fMRI will be acquired with 3.4 x 3.4 x 3.4 mm voxels, TR 2100 ms, TE 30 ms, and flip angle 70°. Two fMRI sequences will be acquired before and after treatment: (1) a 10 minute RS-fMRI, in which subjects will be asked to lie quietly in the scanner and not think of anything in particular; and, (2) a 15 minute task-based fMRI exam during a cigarette craving cue task. fMRI data will be processed and analyzed as described in the methods section (see C.4 through C.8). Briefly, outcome measures will include insular functional connectivity (see **Aim #3**) changes at the whole brain level after treatment compared to before treatment.

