C.5 Image preprocessing: Raw BOLD data will be pre-processed using SPM8 (website: http://www.fil.ion.ucl.ac.uk). After discarding the first four volumes for saturation effects, motion correction will be applied with a 3D rigid body transformation. Subjects with head movement >2mm will be excluded. fMRI images will be spatially normalized to Montreal Neurological Institute (MNI) space by registering each subject's fMRI images to their high resolution T1W scan, which will be registered to MNI space using the DARTEL method. Registered fMRI images will be spatially smoothed using a 4mm FWHM isotropic Gaussian kernel. Band-pass filtering (0.01Hz–0.08Hz) will be applied to reduce effects of low frequency drift and high-frequency physiologic noise. fMRI data will be corrected for movement parameters (3 rotational and 3 translational variables) as well as global, CSF, and white matter signal fluctuations.

C.6 Seed Based Insular Functional Connectivity: Using customized MATLAB scripts, whole brain voxel-wise connectivity maps will be calculated according to Margulies et al. from the 10 minute RS-fMRI exams using a seed-based approach with a 5mm radius sphere centered at the right anterior insular rTMS target. To compare insular connectivity, first we will apply a fixed-effects analysis to each subject's resultant whole-brain insular connectivity maps to investigate individual brain connectivity differences associated with treatment. Treatment and group comparisons will be performed using ANCOVA. These comparisons will provide results for **Aim #2**.

C.7 Craving cue task-based insular activity: After resting state fMRI examinations, all subjects will perform smoking cue/neutral cue craving tasks during a 15 minute fMRI using the aforementioned imaging parameters. We have previous experience using this task to elicit food craving. We will use an identical visual cue paradigm, but will replace the food-cue images with the international smoking image series. Each run will consist of pseudorandom presentations of different smoking-related and food-related images. Between images, participants will be asked to fixate on a cross image for variable duration of time to introduce jitter into the design and improve fit of the generalized linear model (GLM).

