# F.3 Aim 3: Determine if insular TMS alters insular activity:

F.3.1 Statistical Design: Contrast maps of smoking>neutral cues will be analyzed using secondlevel random-effects to compare these contrasts within and between treatment groups using ANCOVA. Two separate task-based analyses will be performed: (1) insular ROI analyses by extracting insular activity from the fMRI with a 5mm radius sphere centered at the insular TMS target, and (2) whole brain analysis. Both analyses will control for multiple comparisons and nuisance variables as we will in Aim #2.

F.3.2 Sample Size and Power Analysis: Hanlon et al. measured fMRI activity changes after rTMS to two separate prefrontal targets, resulting in Cohen's *d* values greater than 2.3. Based on these estimates, our target recruitment goal must be greater than 5 in each arm (total n=10) to detect significant differences with 80% power and 0.05 significance level. Our sample size n=32 (after 10% attrition of fMRI data, 10% attrition of TMS administration) is similar or larger compared to other studies using similar methods. With a sample size of 32, we can detect a correlational effect size as small as 0.30 ( $f^2$ ) with 80% power and 0.05 significance level.

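### The Aim 2 and Aim 3 imaging analyses name age as the only covariate and do not write out the outcome variable or the between-arm contrast that tests H2 and H3.

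*Combined protocol and SAP*

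**What the plan says.** H2 and H3 (section I) are both framed against sham. Section IV.A.2 has resting-state and task fMRI acquired before and after rTMS, so a pre-rTMS value is planned for every subject.

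- **Aim 2, F.2.1:** the second-level model will "compare insular connectivity by treatment and group using ANCOVA". On covariates: "Age will be controlled for as nuisance variables".
- **Aim 2, C.6:** each subject's connectivity maps first go through a fixed-effects step "to investigate individual brain connectivity differences associated with treatment". Then: "Treatment and group comparisons will be performed using ANCOVA".
- **Aim 3, F.3.1 (C.7 is similar):** the smoking-over-neutral contrast maps go into a random-effects analysis "to compare these contrasts within and between treatment groups using ANCOVA". Covariates carry over from Aim 2: "Both analyses will control for multiple comparisons and nuisance variables as we will in Aim #2".
- **Outcome definition, IV.A.2:** connectivity outcomes are "changes at the whole brain level after treatment compared to before treatment".

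By comparison, F.1.1 (Aim 1) names the treatment-by-time interaction and the test statistic for it.

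**The concern.** H2 and H3 each need one between-arm test. The imaging sections do not say whether the second-level outcome is the post-rTMS value, the change, or both scans as repeated measures. Nor do they say which contrast decides the hypothesis. The cluster correction in F.2.1 controls error over voxels; it does not cover a choice among contrasts made after the data are seen.

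The gap is wider for Aim 3. Its text has no subject-level pre-post step and gives no priority between the within-arm and between-arm comparisons.

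The pre-rTMS scan is collected but nowhere named as a covariate. With about 16 analysable subjects per arm, that gives up precision that needs no extra scanning. It matters because section G plans to read an absence of differences as evidence that the insula is less critical than the literature suggests. That inference needs a named between-arm test with the best precision available.

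**Working it through.** **1. The plan's own figures.** Two-sample t-test, two-sided 0.05 (sidedness is not stated, so this is an assumption). Noncentrality = d × √(n/2), df = 2n − 2.

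- Aim 2, d = 1.9: power is 74.9% at 5 per arm and 84.2% at 6. F.2.2 gives 6.
- Aim 3, d = 2.3: power is 77.3% at 4 per arm and 88.8% at 5. F.3.2 gives 5.
- Attrition: 40 × 0.9 × 0.9 = 32.4, so 32 in total, or 16 per arm.

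These sizes reproduce as plain two-group calculations with no baseline term and no pre-post correlation. The separate f² = 0.30 at n = 32 was not matched (80% power needs 0.262 with one predictor and 0.334 with two). Nothing below depends on it.

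**2. Inputs for the comparison.** 16 per arm and 80% power come from F.2.2 and F.3.2. The pre-post correlation r is not in the documents; 0.3, 0.5 and 0.7 are assumed. Pre and post SDs are taken as equal, and age is left out throughout.

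**3. Variance of the arm comparison, in single-scan variance units.**

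- Post-rTMS value only: 1
- Change score: 2(1 − r)
- Post adjusted for pre: 1 − r²
- Adjusted over change: (1 − r²) / [2(1 − r)] = (1 + r)/2, which is below 1 whenever r < 1

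For r = 0.3, 0.5, 0.7 that ratio is 0.65, 0.75, 0.85. Its inverse is 1.54, 1.33, 1.18, so adjustment is worth about 54%, 33% and 18% more subjects than the change score.

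**4. Detectable difference at 16 per arm.** With 30 df the detectable standardized difference is 1.024. With 29 df, after spending one on the covariate, it is 1.025. Multiply by the square root of the variance factor:

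| Assumed r | Post only | Change score | Baseline-adjusted |
|---|---|---|---|
| 0.3 | 1.02 | 1.024 × √1.4 = 1.21 | 1.025 × √0.91 = 0.98 |
| 0.5 | 1.02 | 1.024 × √1.0 = 1.02 | 1.025 × √0.75 = 0.89 |
| 0.7 | 1.02 | 1.024 × √0.6 = 0.79 | 1.025 × √0.51 = 0.73 |

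**5. The same in power.** At a true difference of 1.02 SD, post-only power is 80%. Change-score power is 66%, 80% and 95% for the three values of r; baseline-adjusted power is 84%, 90% and 97%.

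**6. Limits.** The adjusted column allows for the lost degree of freedom but not for chance baseline imbalance between arms. That imbalance widens the interval slightly and could offset the gain only when r is close to 1. The table describes a single test at 0.05. F.2.1 uses a voxel-wise threshold of 0.005 with family-wise cluster correction, so the SD figures do not transfer to the maps. They fit the Aim 3 region-of-interest mean best.

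**The case against.** The best defence is that the intended analysis can be read from the whole document. IV.A.2 defines the connectivity outcome as a change. C.6 derives a within-subject difference before any group comparison, and inside one subject treatment can only mean before against after. Both hypotheses are set against sham. For Aim 2 this stands: a change compared between arms is the natural reading.

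A reader might therefore go too far in inferring any of the following:

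- **That the plan excludes a pre-post contrast between arms.** It does not. The contrast is unwritten, and for Aim 2 the text points towards it.
- **That H2 or H3 will be judged on a group main effect averaging the pre and post scans.** No section names such a test as decisive.
- **That a within-arm change will decide H3.** F.3.1 plans between-arm comparisons too. The sham d of 1.9 in F.1.2 is a craving figure from a cited study of another target, so it does not show how far fMRI measures move under sham.

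It can also be said that change scores and baseline adjustment are both unbiased under randomization, that the gain shrinks as r rises (0.647 against 0.615 SD at r = 0.8), and that the planning effects of 1.9 and 2.3 exceed every detectable difference in the table. The first two are correct. The third helps only if effects taken from a cited study of prefrontal targets apply here on the single-scan scale, which the documents do not establish.

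None of this supplies the missing dependent variable and contrast, or the missing pre-post step for Aim 3.

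**Conclusion.** The point holds as under-specification plus an avoidable loss of precision; it is not a bias. F.2.1 and F.3.1 leave the dependent variable and the deciding between-arm contrast unwritten and adjust only for age. For Aim 2 the intended test can be inferred. For Aim 3 it cannot, and within-arm comparisons sit beside between-arm ones without priority.

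On the favourable reading, omitting the pre-rTMS value raises the detectable difference by 0.23, 0.13 (1.024 − 0.888 = 0.136 before rounding) and 0.06 SD at r = 0.3, 0.5 and 0.7. This rests on the assumed r, equal pre and post SDs, 16 per arm and a single two-sided 0.05 test. The direction does not depend on the particular r, short of values close to 1. The change is worth making because it costs almost nothing.

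**What to change.** In F.2.1 and F.3.1, with C.6 and C.7 brought into line, state that:

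1. H2 and H3 are each tested by the between-arm difference (active minus sham) in the post-rTMS value, with the pre-rTMS value of the same measure and age as covariates.
2. The Aim 3 region-of-interest mean takes the pre-rTMS mean as its covariate.
3. Voxel-wise maps take the pre-rTMS map as a voxel-wise covariate. If the software cannot do this, the post-minus-pre map is compared between arms, accepting the lower precision.
4. Within-arm changes are descriptive and do not test H2 or H3.

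Cost: a few sentences and one degree of freedom. No new scans, visits or subjects are needed.

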Task-based fMRI exams will be preprocessed as above. Data will be modeled in SPM8 using a GLM with customized square waveforms representing the condition (i.e., cigarette versus neutral stimulus) and duration of stimulus convolved with a canonical hemodynamic response function.

Contrast maps of smoking>neutral cues will be analyzed using second-level random-effects to compare these contrasts within and between treatment groups using ANCOVA. Two separate task-based analyses will be performed: (1) insular ROI analyses by extracting insular activity from the fMRI with a 5mm radius sphere centered at the insular TMS target, and (2) whole brain analysis. Both analyses will control for multiple comparisons using cluster-based correction for family-wise error p<0.05. These comparisons will provide results for **Aim #3**.

C.8 Resting state network analysis (secondary): One inherent limitation of the seed-based connectivity approach is that the resultant connectivity maps are highly dependent upon ROI selection. To circumvent the potential interference caused by seed selection, secondary investigation of the functional connectome will be performed using group independent component analysis to make inferences using the GIFT toolbox (http://icatb.sourceforge.net) and using the same method and analysis pipeline as our preliminary data. Resultant resting state network connectivity maps will be compared by group to investigate differences in strength and direction of connectivity between salience, default mode, and executive control networks.

C.9 Brain-behavior relationships (secondary): Secondary analysis of brain-behavior relationships will be conducted using a GLM in SPM8 by regressing insular connectivity and activity (see C.3.6) against craving and dependence measures. This will characterize the relationship between behavior (**Aim #1**) and brain function (insular connectivity [**Aim #2**] and activity [**Aim #3**]).

C.10 Relative concentrations of GABA, glutamate, and glutamine after rTMS (exploratory): Exploratory analysis of the changes in GABA, glutamate, and glutamine concentrations induced by rTMS will be performed using spectroscopic peak detection methods and ANCOVA.

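### The whole-brain maps claim 5% family-wise error from a Monte Carlo cluster threshold at voxel p<0.005 whose spatial noise model is not stated; a permutation threshold would make the claim dependable at little cost.

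*Combined protocol and SAP*

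**What the plan says.** F.2.1 gives the Aim 2 model: "A second-level random effects model will be used to compare insular connectivity by treatment and group using ANCOVA", with age as the nuisance variable. On multiplicity it says "A Monte Carlo cluster correction threshold will be applied to correct for multiple comparisons", "using a voxel-wise p<0.005 and family-wise p < 0.05". F.3.1 applies the same rule to Aim 3 by reference: "Both analyses will control for multiple comparisons and nuisance variables as we will in Aim #2". Section C.7 is less specific: "Both analyses will control for multiple comparisons using cluster-based correction for family-wise error p<0.05", with no voxel-level cut.

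Two features of the images bear on cluster size. Section A.2 says they are "acquired with 3.4 x 3.4 x 3.4 mm voxels", and C.5 says "Registered fMRI images will be spatially smoothed using a 4mm FWHM isotropic Gaussian kernel". That kernel is the only Gaussian element described. It is a preprocessing step, not a model for the residual noise.

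For the trial analysis, the documents do not name the Monte Carlo program, the spatial autocorrelation model, the smoothness estimate, the search mask, the cluster extent or the sidedness. The only extent given is in section III, for the single-subject pilot: more than 23 voxels at the same voxel and family-wise levels. No permutation test is planned.

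**The concern.** A Monte Carlo extent threshold is the 95th percentile of the largest cluster in simulated noise, so it is only as good as that noise. At a cluster-forming cut as lenient as p<0.005, the size of the largest null cluster depends strongly on how far correlation extends beyond neighbouring voxels. A simulation matched to short-range smoothness, but with tails that fall off too fast, gives an extent that is too small and lets too many chance clusters through.

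The seed-based whole-brain map is the primary Aim 2 analysis, and the whole-brain map is one of two Aim 3 analyses. Section G expects positive findings to lead to further studies, so a chance cluster reported as a connectivity change could steer later work.

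**Working it through.** **The plan's own figure.** The stated 5% cannot be reproduced exactly, because smoothness, mask, extent and sidedness are not given. It can be tested under stated assumptions.

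**Inputs from the documents.** Voxel size 3.4 mm (A.2); voxel p<0.005 and family-wise 0.05 (F.2.1); 32 analysed subjects (F.2.2), taken as 16 per arm.

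**Assumed inputs.** An ellipsoid mask of 38,104 voxels (38,104 × 3.4³ mm³ = 1.50 L); 18-neighbour clusters; a one-sided contrast; 16 v 16 two-sample t maps with 30 degrees of freedom and age omitted. The noise autocorrelation at distance r mm was either Gaussian with FWHM 8 mm, or mixed:

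ρ(r) = a·exp(−r²/(2·3.4²)) + (1−a)·exp(−r/10), with a = 0.9, 0.7 or 0.5.

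**Matching the Gaussian model.** The Gaussian was fitted to the one-voxel correlation: s = 3.4/√(−4 ln ρ(3.4)), FWHM = 2.355·s. For a = 0.7:
- ρ(3.4) = 0.7 × 0.607 + 0.3 × 0.712 = 0.638, so s = 2.54 mm and FWHM = 6.0 mm.
- At 10 mm the mixed noise has correlation 0.7 × 0.013 + 0.3 × 0.368 = 0.120.
- At 10 mm the matched Gaussian has exp(−100/(4 × 2.54²)) = 0.02.

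The two models agree at one voxel and differ about six-fold at 10 mm.

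**Results at voxel p<0.005.** Extents come from 2,000 Monte Carlo maps, error rates from 400 null trials per row, and the permutation test used 59 label shuffles per trial. Brackets are 95% confidence intervals.

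| Noise | Gaussian-matched extent (voxels) | Error with that extent | Extent from true autocorrelation | Error with that extent | Error with permutation |
|---|---|---|---|---|---|
| Gaussian, 8 mm | 34 | 2.8% (1.4–4.9) | 34 | 2.8% | 5.5% (3.5–8.2) |
| Mixed, a = 0.9 | 16 | 5.8% (3.7–8.5) | 19 | 1.5% | 3.7% (2.1–6.1) |
| Mixed, a = 0.7 | 18 | 18.0% (14.4–22.1) | 27 | 3.3% | 4.3% (2.5–6.7) |
| Mixed, a = 0.5 | 19 | 35.5% (30.8–40.4) | 41 | 3.8% | 4.8% (2.9–7.3) |

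At voxel p<0.001, the Gaussian-matched extent gave 2.8%, 4.8% and 9.8% in the three mixed settings. The lenient cut therefore accounts for much of the inflation.

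**Repeats with other settings.** One-sided z-fields on 38,061 voxels gave 2.8% under Gaussian noise and 6.8%, 27.5% and 41% as the tails lengthened. Two-sided fields on about 39,900 voxels gave 4% under Gaussian noise and 19–21% with 20–40% weight on an exponential tail of 8–12 mm decay. A re-run of those long-tailed settings with 800 maps each gave 11–25%. Across all of these the range is about 3% to 40%.

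**The pilot's extent.** At 3.4 mm voxels, a Gaussian simulation gives an extent of 8 voxels at 4 mm FWHM, 21 at 6.5 mm and 25 at 7 mm one-sided, and 24 at 8 mm two-sided. The pilot's figure of more than 23 voxels is therefore compatible with a Gaussian simulation, but does not show that one was used.

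**Is permutation feasible?** With 16 per arm there are 32!/(16!·16!) = 601,080,390 relabellings between arms and 2¹⁶ = 65,536 sign patterns within an arm, ample for 5,000 draws.

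**The case against.** The strongest objection is that the Gaussian model is not in the documents. A reader might infer that the plan uses one and that its true error is therefore several times 5%. The text supports neither step: it says only that a Monte Carlo threshold will be used. A reader might also infer that such a threshold holds 5% only under Gaussian correlation. The table contradicts this, since Monte Carlo with the true long-tailed autocorrelation gave 1.5–3.8%. Both points stand.

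The size of the inflation also follows from tail weights and decay lengths that have no source in the documents. C.5 removes global, CSF and white-matter signal, which the simulations do not model. This stands too.

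The pilot extent cuts both ways. Applied to the two-sided long-tailed fields, more than 23 voxels gave 0.8–2.9% error, against 11–25% with Gaussian-matched extents of 12–15 voxels. In the one-sided setting, however, its 24-voxel minimum falls short of the 27 and 41 voxels needed at a = 0.7 and a = 0.5. It comes from one subject, the voxel size and smoothness of that scan are not given, and the plan does not say it will be used in the trial.

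Finally, permutation has assumptions of its own. Randomisation supports exchangeable labels between arms, but an age covariate makes the test approximate. Permuting labels cannot test the within-group contrasts in F.3.1.

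**Conclusion.** The concern holds in a limited form. As written, the 5% family-wise level for the Aim 2 map and the Aim 3 whole-brain map is not assured, because it depends on an unstated noise model. If that model is Gaussian and the real tails are long, the error could lie anywhere from near 5% to about 40% under the settings tried. A mild departure from Gaussian costs little (5.8% and 6.8% in the two runs at the mildest setting). The documents do not allow an estimate for this trial.

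A reader might go further and treat Aims 2 and 3 as a whole as unreliable. The documents do not support that. The Aim 3 ROI analysis is unaffected if it tests one averaged value for the sphere, the secondary network analysis in C.8 is separate, and the craving outcome of Aim 1 does not use this correction.

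This is a cheap improvement: in the simulations, permutation at the plan's own voxel cut gave 3.7–5.5% in every setting, with every interval including 5%.

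**What to change.** In F.2.1 and the whole-brain part of F.3.1, keep voxel p<0.005 and family-wise 0.05 and obtain the cluster extent by permutation:

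- **Between-arm contrast:** permute arm labels on the pre-to-post change maps, with age as the nuisance term (Freedman-Lane), using at least 5,000 permutations and the distribution of the largest cluster. State the sidedness. Change maps match the outcome in A.2 and add no covariate to F.2.1.
- **Within-group contrasts:** use sign-flipping of the change maps, and state that this assumes symmetric errors.
- **If Monte Carlo is kept:** name the program and mask, use a non-Gaussian autocorrelation model estimated from the residuals, and state the sidedness, all before unblinding.

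Bring C.7 into line so that it gives the same rule as F.3.1.

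The cost is a few sentences in the plan and some hours of computing. The extent may be larger, so fewer clusters may survive. For scale, the extent from the true autocorrelation in the long-tailed simulations was 19, 27 and 41 voxels, where the Gaussian match gave 16, 18 and 19.

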# F. Data Analysis Plan:

# F.1 Aim 1: Determine if insular TMS reduces cigarette craving:

F.1.1 Statistical Design: For a multivariate analysis of covariance model, we will fit a general linear multivariate model, with measures of craving before and after treatment as the outcomes. As predictors, we will fit indicator variables for treatment assignment, and FTND. We will use the Hotelling-Lawley test to assess treatment by time interaction, and the main effects of time and treatment.

F.1.2 Sample Size and Power Analysis: Li et al. conducted an experiment similar to ours, measuring craving responses to DLPFC rTMS (Cohen's d = 3.0) or sham TMS (Cohen's d = 1.9).

Based on these estimates, we will need to recruit 15 subjects to each arm (total n=30) to detect similar differences with 80% power and 0.05 significance level. Our study should achieve similar power, even with up to 25% loss to follow-up in each arm. If our loss-to-follow up is only 10% per arm, we can detect an effect size as small as 0.962 with 80% power and 0.05 significance level. Our sample size is larger or similar to other studies using similar methods.

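### Section G reads a null result as evidence that the insula matters less than reported, but the planned sample cannot support that, and F.2.2 and F.3.2 give no clear active-versus-sham imaging effect to read a null against

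*Combined protocol and SAP*

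**What the plan says.** H2 and H3 in section I are both comparisons of insular rTMS with sham.

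The imaging power statements take their effect sizes from one cited study. F.2.2 says it "measured fMRI connectivity changes after rTMS to two separate prefrontal targets" with d above 1.9, and concludes that "our target recruitment goal must be greater than 6 in each arm (total n=12) to detect significant differences with 80% power". F.3.2 says it "measured fMRI activity changes after rTMS to two separate prefrontal targets" with d above 2.3, and concludes that "our target recruitment goal must be greater than 5 in each arm (total n=10) to detect significant differences with 80% power". Neither section mentions a sham condition for those values.

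Both sections then give an expected analysed sample of 32 and say that with it "we can detect a correlational effect size as small as 0.30" (f²). No predictors are named. The only analysis in the plan that is plainly correlational is the secondary one in C.9, "regressing insular connectivity and activity (see C.3.6) against craving and dependence measures".

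For craving, F.1.2 quotes separate active (3.0) and sham (1.9) values and adds that, at 10% loss, "we can detect an effect size as small as 0.962 with 80% power and 0.05 significance level".

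Section G fixes the reading of a null in advance. If neither craving nor fMRI differs, the insula will be judged a less important node than published work suggests, and later work will turn to prefrontal targets. It attaches no detectable effect and no confidence interval to that reading.

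**The concern.** A non-significant test says that the data are compatible with no effect. It supports a small or absent effect only if the interval around the estimate excludes effects that would matter. Section G skips that step.

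The reader then needs to know what active-versus-sham difference each aim could detect. For craving, F.1.2 supplies one. For imaging, F.2.2 and F.3.2 offer sample-size minima based on post-stimulation changes and a correlational f², neither of which is clearly a difference from sham. A reader who takes 6 and 5 per arm at face value would think 16 per arm very sensitive, and would accept a null as strong evidence against the insula. At stake is an unsound scientific conclusion, and the redirection of later research that section G ties to it.

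**Working it through.** **Inputs.** 20 per arm (section I). Imaging attrition of 10% and then 10% (F.2.2, F.3.2): 40 × 0.9 × 0.9 = 32.4, stated as 32, taken here as 16 per arm. Alpha 0.05 and power 80% (F.2.2, F.3.2). Sidedness is not stated; two-sided is assumed.

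**Method.** Two-sample t-test with n per arm: df = 2n − 2, noncentrality = d × √(n/2), power from the noncentral t distribution.

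**1. The plan's own minima reproduce.**

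| Input d | n per arm | Power |
|---|---|---|
| 1.9 | 5 | 74.9% |
| 1.9 | 6 | 84.2% |
| 2.3 | 4 | 77.3% |
| 2.3 | 5 | 88.8% |

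The smallest sizes reaching 80% are 6 and 5 per arm, as stated. The arithmetic is right, and the match indicates that values described as changes after rTMS were entered as between-arm differences.

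**2. Aim 1, for contrast.** The difference between the active and sham values is 3.0 − 1.9 = 1.1. At 15 per arm this gives 82.8% power (14 per arm gives 79.99%), matching the stated 15. With 10% loss, 20 × 0.9 = 18 per arm, and the detectable d is 0.961 against the stated 0.962. So the craving figures can be read as active versus sham.

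**3. What f² = 0.30 could mean at n=32.**
- Simple correlation by Fisher z: r = tanh((1.960 + 0.842)/√29) = 0.478, so f² = r²/(1 − r²) = 0.296, which rounds to 0.30.
- Two-group contrast: the detectable f² is d²/4 = 1.024²/4 = 0.262.
- Taking 0.30 itself as a two-group contrast: d = 2√0.30 = 1.10, with 85% power at 16 per arm.

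The figure fits a correlation better, in line with its label, but it can be converted to a two-group effect. It is ambiguous.

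**4. Active versus sham at 16 per arm, single two-sided 0.05 test.**
- The d detectable with 80% power is 1.02.
- Power is 27.8% at d=0.5, 59.1% at d=0.8 and 78.1% at d=1.0.
- A true d of 0.8 would be missed about 41% of the time, and a true d of 0.5 about 72% of the time.
- 95% interval half-width: t(0.975, 30) × √(2/16) = 2.042 × 0.3536 = 0.72.

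**5. Units.** These d values and the 0.72 are in SDs of the analysed change score. In SDs of a single measurement the half-width is 0.72 × √(2(1 − r)), where r is the pre-post correlation. The documents do not give r. Over an assumed range it is about 0.85 at r=0.3, 0.72 at r=0.5 and 0.46 at r=0.8.

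**6. Multiplicity.** Aim 2 is a whole-brain analysis, and C.7 and F.3.1 apply multiple-comparison control to both Aim 3 analyses, the insular ROI included. The 1.02 is therefore a best case. It fits the ROI only if the sphere is averaged to one value and tested once, which the plan does not say. Cluster-corrected tests are expected to need a larger effect.

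**The case against.** The strongest defence has four parts.

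*Section G most naturally describes a joint null.* This stands. A reader might infer that a null on imaging alone would be held against the insula; the text does not go that far. Section E also foresees an effect on connectivity without one on activity, and looks at both for that reason. But a joint null does not rescue the inference: the craving test is sized for d of about 0.96 and the imaging tests, at best, for about 1.02, so smaller effects could be missed on all of them.

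*A detectable effect at n=32 is stated.* This stands in part. Converted to two groups, f² of 0.30 is d of about 1.10, close to 1.02. It would be too strong to say that the plan gives no figure. It gives one whose meaning is unclear.

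*The cited study may have been sham-controlled.* The documents do not settle this. A reader might infer that 1.9 and 2.3 are uncontrolled and so wrong; only *not shown to be between-arm effects* is supported. It is also tempting to borrow the craving ratio, 1.9/3.0 = 63%, as the sham share of the imaging response. Nothing in the documents supports carrying it over.

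*The minima do not drive enrolment.* This stands. Aim 1 has the largest requirement (15 per arm), and 20 per arm are planned.

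**Conclusion.** The point holds as a minor one about interpretation. Section G's rule turns non-significance into a substantive conclusion that about 16 evaluable imaging participants per arm cannot carry: 80% power only from d of about 1.02, and an interval of about ±0.72 SD of change. F.2.2 and F.3.2 give no clear active-versus-sham figure that would let a reader see this.

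It should not be read as a finding that the sample is too small. If 1.9 and 2.3 do hold between arms, 16 per arm gives more than 99.9% power for both in a single 0.05 test.

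The figures assume a two-sided test, an equal split of 32, one test per measure and change-score SD units. If baseline were used as a covariate, the detectable difference in SDs of a single measurement would be about 0.89 at an assumed pre-post correlation of 0.5 and 0.73 at 0.7. That would improve sensitivity but would not make a null informative about small effects.

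**What to change.** 1. In section G, replace the null interpretation with: *If no differences are observed, results will be reported as active-minus-sham differences with 95% confidence intervals and read against the detectable differences for each aim; a null result does not exclude smaller effects and does not by itself show that the insula is less critical.*

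2. In F.2.2 and F.3.2, add: *With 16 evaluable per arm, a single two-sided 0.05 active-versus-sham test has 80% power for d of about 1.02 in SDs of change. This is a best case, which applies to the Aim 3 ROI only if it is averaged to one value and tested once; cluster-corrected analyses are expected to need a larger effect.* No single-voxel figure should be written in, since that is not the planned test.

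3. Remove the 6 and 5 per arm statements, or justify 1.9 and 2.3 as active-minus-sham effects. Say which analysis f² of 0.30 refers to.

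Item 3 alone would not cure the problem; the section G sentence has to change.

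The cost is a less favourable stated sensitivity, a weaker conclusion from a null, and the reporting of confidence intervals. Sample size, endpoints and tests stay as they are.
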